2. STATISTICAL HYPOTHESES

The primary efficacy endpoint is the change from baseline in MADRS total score to end of Day 28. The hypothesis of this study is that esketamine nasal spray, 56 mg or 84 mg, when used as monotherapy, is superior to placebo nasal spray in improving depressive symptoms in participants with TRD.

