5.3. Primary Endpoint Analysis

The multiplicity, with regard to testing multiple endpoints (the primary [Day 28] and the key secondary [Day 2]) and multiple doses (esketamine 84 mg vs placebo and esketamine 56 mg vs placebo), will be controlled by a sequential gatekeeping method using the Hochberg procedure, a familywise error rate of 0.05 and a truncation parameter of 1. For the primary hypothesis (Day 28), if the largest p-value of the two dose comparisons of esketamine 84 mg vs placebo and esketamine 56 mg vs placebo is less than two-sided 0.05 level, both esketamine 56 mg and esketamine 84 mg will be declared statistically significantly different from placebo. If the largest p-value of primary endpoint tests is greater than or equal to 0.05, the comparison associated with this p-value will be declared not statistically significant and the smaller p-value will be compared to the 0.025 level. The key secondary hypothesis (Day 2) will be tested using the Hochberg procedure only if the null hypothesis for the primary endpoint is rejected for both doses.

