5.3.2. Primary Estimand

Primary Trial Objective: To evaluate the efficacy of each individual dose of esketamine nasal spray, 56 mg and 84 mg, compared with placebo nasal spray in improving depressive symptoms in participants with TRD who have met nonresponse criteria, as assessed by the change from baseline in the Montgomery-Asberg Depression Rating Scale (MADRS) total score from Day 1 (prerandomization) to end of the 4-week double-blind treatment phase (Day 28).

Estimand Scientific Question of Interest: What is the antidepressant benefit from each individual dose (56 mg and 84 mg) of esketamine nasal spray compared with placebo nasal spray in improving depressive symptoms in participants with TRD who have met nonresponse criteria based on the change in the Montgomery-Asberg Depression Rating Scale (MADRS) total score from Day 1 (prerandomization) to end of the 4-week double-blind treatment phase (Day 28) if the participants take study intervention as directed?

The primary estimand is defined by the following 5 components:

Study Intervention:

• Experimental: esketamine 56 mg, esketamine 84 mg

• Control: Placebo

Population: Participants with TRD who have met the inclusion/exclusion criteria and the nonresponse criteria

Variable: Change from baseline to Day 28 in the MADRS total score

Summary Measure: Difference in means between each dose and placebo for the change from baseline in MADRS total score at Day 28.

Intercurrent events and their corresponding strategies:

Intercurrent Events	Name of Strategy for Addressing Intercurrent Events and Its Description
Premature discontinuation of the randomized treatment with or without a switch to alternative antidepressant	Hypothetical strategy: as if the intercurrent event had not occurred
treatment	

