5.3.2.1.2. Sensitivity Analysis

To evaluate the robustness of the MMRM analysis to increasing deviations from the MAR assumption, a delta adjustment multiple imputation method will be implemented on the MADRS total score if the results from the primary analysis show a significantly greater improvement in

MADRS total score at Day 28 in each dose of esketamine nasal spray compared to placebo. (National Research Council 2010; Permutt 2015)

This method will employ the following 3 steps:

Step 1 – Multiple Imputation (MI)

Missing at random (MAR) is assumed for intermediate missing data (ie, missing data between non-missing observations). If there are participants with a non-monotone missing data pattern, datasets with only monotone missing data patterns will be created first by imputing the intermediate missing values using methods such as the MCMC (Markov Chain Monte Carlo) method. Five hundred (500) imputations will be performed to create 500 unique datasets which now have monotone missing (ie., missing data after the participant experienced an intercurrent event) data pattern. This will be done using SAS PROC MI and the MCMC statement with the following specifications (in case of non-convergence, analysis center will be removed from the following model):

```
PROC MI DATA=INPUT NIMPUTE=500 SEED=234 OUT=IN MCMC;
```

VAR ...; (intervention group, analysis center, antidepressant treatment status, and the preceding non-missing values in the order of clinical visits: baseline, Day 2, Day 8, Day 15, Day 22 and Day 28)

MCMC CHAIN=SINGLE NBITER=200 NITER=100 IMPUTE=MONOTONE; RUN;

Monotone missing data will first be imputed by MAR-based MI regression, and the imputed scores in the experimental intervention groups will be adjusted to be worse than the other participants in same group with non-missing data as discussed below. The multiple imputation will be performed using SAS PROC MI with the MONOTONE statement and the REGRESSION option with the following specifications (in case of non-convergence, analysis center will be removed from the following model):

```
PROC MI DATA=IN_MCMC NIMPUTE=1 (see note) SEED=234 OUT=OUTPUT; BY IMPUTATION;
```

VAR ...; (intervention group, analysis center, antidepressant treatment status, and the preceding non-missing values in the order of clinical visits: baseline, Day 2, Day 8, Day 15, Day 22 and Day 28)

CLASS ...; (intervention group, analysis center, antidepressant treatment status) MONOTONE REGRESSION;

RUN:

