*Note: NIMPUTE=500 if MCMC was NOT applied at the previous step.

The imputed values for subjects who discontinued DB treatment [QX[1]]will be adjusted by adding δ_c to the imputed values for participants randomized to the control group and adding δ_A to the imputed values for participants randomized to the experimental intervention groups. Delta-adjusted fully imputed datasets will be generated for different combinations of δ_c and δ_A values as defined below:

- $\delta_c = 0$ and $\delta_A = 0$ to Δ^* in increments of 1 (experimental group-only adjustment analysis)
 - Adding positive values results in higher (worse) scores. Δ* represents the adjustments leading to the 'tipping point', so the smallest delta adjustments values at which conclusions change from favorable (ie, statistically significant: 2-sided p-values for both doses ≤0.05 in favor of esketamine, or the smaller 2-sided p-value ≤0.025 in favor of esketamine) to unfavorable (fail to reject the null hypothesis of no intervention difference).

These methods will be applied to all missing data under hypothetical strategy.

Step 2 – Analysis

Same MMRM analysis as described for the primary efficacy analysis (Section 5.3.2.1.1) will be performed for each set of the adjusted fully imputed datasets.

Step 3 – Pooling

Rubin's methodology will be applied to the MMRM results from the 500 imputed datasets to produce final inferences. (Rubin 1987)

Between-group comparisons to placebo at Day 28 (eg, 2-sided p-values, point estimates for intervention difference) will be displayed for each considered δ_A , up to the 'tipping point' adjustment.

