5.3.3. Supplementary Estimand

All components as described under Primary Estimand (Section 5.3.2) apply to the Supplementary Estimand except the strategy for addressing intercurrent events.

Intercurrent events and their corresponding strategies:

	Name of Strategy for Addressing Intercurrent Events
Intercurrent Events	and Its Description
Premature discontinuation of the randomized treatment	Treatment policy strategy: all observed values of the
with or without a switch to alternative antidepressant	endpoint are used regardless of whether or not the
treatment	participant had experienced this intercurrent event

The treatment policy strategy attempts to estimate the treatment effect irrespective of the intercurrent event. Therefore, post-treatment observations will be used in the analysis for those participants who discontinued study intervention.

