5.3.3.1. Analysis Methods

This method will employ the following 3 steps:

Step 1 – Multiple Imputation (MI)

Once monotone missing datasets are created after imputing intermediate missing data using the MCMC method as described in Section 5.3.2.1.2, the monotone missing data will be imputed using the Copy Reference (CR) MI method for the primary analysis as a supplementary analysis.

Missing not at random (MNAR) is assumed for monotone missing (i.e., missing data after the occurrence of an intercurrent event under treatment policy) in the experimental intervention group, where efficacy scores are assumed as if participant had always been in the control group. MAR is assumed for missing data in the control group.

The efficacy data that is either missing or not used after the intercurrent event at a given timepoint will be imputed using the imputation model of the control group, i.e., conditional on the data observed or imputed at previous timepoints relative to the mean of the model for the control group.

This approach does not assume a sustained benefit of experimental intervention for the efficacy data that is either missing or not used after the intercurrent event, and uses an imputation method that is based on the control group distribution and the estimated correlations between time points in the control group.

Step 2 – Analysis

Same MMRM analysis as described for the primary efficacy analysis (Section 5.3.2.1.1) will be performed for each set of the adjusted fully imputed datasets.

Step 3 – Pooling

Rubin's methodology will be applied to the MMRM results from the 500 imputed datasets to produce final inferences. (Rubin 1987)

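### The tipping-point analysis is triggered by a win for both doses but tips only when the last dose is lost, so a one-dose win may get no analysis and the weaker dose has no tipping point of its own

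*SAP*

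**What the plan says.** Four parts of the SAP bear on this.

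- **Primary decision rule (SAP 5.3).** Hochberg is applied across the two doses at Day 28. If the larger p-value fails at 0.05, "the comparison associated with this p-value will be declared not statistically significant and the smaller p-value will be compared to the 0.025 level". A one-dose success is therefore a possible outcome of the trial.
- **Trigger for the delta analysis (SAP 5.3.2.1.2, opening paragraph).** The delta-adjusted multiple imputation is run if the primary analysis shows significantly greater improvement in "MADRS total score at Day 28 in each dose of esketamine nasal spray compared to placebo".
- **Definition of the tipping point (SAP 5.3.2.1.2, Step 1).** One δ_A, raised in steps of 1 point, is added to the imputed values in both esketamine arms. Placebo is left unadjusted. Δ* is the smallest value at which the conclusion stops being favorable, where favorable means "2-sided p-values for both doses ≤0.05 in favor of esketamine, or the smaller 2-sided p-value ≤0.025 in favor of esketamine".
- **Display (SAP 5.3.2.1.2, Step 3).** "Between-group comparisons to placebo at Day 28 (eg, 2-sided p-values, point estimates for intervention difference) will be displayed for each considered" value on the grid. The display stops at Δ*.

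The hypothesis in SAP 2 is worded as an alternative: "The hypothesis of this study is that esketamine nasal spray, 56 mg or 84 mg". The objective in SAP 5.3.2 is worded per dose: "To evaluate the efficacy of each individual dose of esketamine nasal spray, 56 mg and 84 mg, compared with placebo nasal spray".

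**The concern.** The trigger and the tipping criterion use different definitions of success. The trigger, read literally, needs both doses. The tipping criterion needs only one.

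Two consequences follow. First, if only one dose wins, the literal trigger is not met. The claim for that dose then has no tipping-point check of the missing-at-random assumption behind the primary hypothetical estimand. Second, if both doses win, the single Δ* marks the loss of the last remaining rejection. It can be larger than the delta at which the weaker dose's claim fails, yet it is the only tipping point the SAP defines.

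Each dose can be claimed separately, so the robustness statement should be available for each dose claimed.

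**Working it through.** **Inputs.** From SAP 3: difference 5.4 points, SD 12, 71 completers per esketamine arm and 142 on placebo, two-sided familywise 0.05, 20% drop-out. From Protocol 2.2: TRD3001 differences of 4.1 (56 mg) and 3.2 (84 mg). Assumed: SD 12 also in the TRD3001 scenario; the same imputed share f in both active arms, with f = 0.20 (the planned drop-out rate) or 0.10; and a standard error that does not change with delta.

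**Step 1: reproduce the plan's power.** SE = 12 × √(1/71 + 1/142) = 1.744. The two contrasts share the placebo arm and have correlation 71/(71 + 142) = 1/3. Simulating three normal arm means with a pooled SD on 281 df and applying Hochberg gives 85.6% per dose and 93.6% for at least one dose. The SAP states 85% and 93%, so its figures reproduce.

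**Step 2: how often exactly one dose wins.** The stated figures already imply it: both = 2 × 85 − 93 = 77%, exactly one = 93 − 77 = 16%. By simulation:

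| True differences | At least one | Both | Exactly one | Exactly one, given success |
|---|---|---|---|---|
| 5.4 / 5.4 | 93.6% | 77.5% | 16.1% | 17.2% |
| 4.1 / 3.2 | 65.8% | 34.1% | 31.7% | 48.2% |

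**Step 3: what Δ* measures.** Hochberg rejects the dose with the smaller p-value exactly when both p-values are at most 0.05 or the smaller is at most 0.025. That is the SAP's favorable condition, so Δ* is the point at which this dose's rejection is lost. The other dose's rejection is lost as soon as its own p-value passes 0.05.

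**Step 4: size of the gap for given observed differences.** Adding δ_A to a share f of the active-arm values reduces the observed difference by f × δ_A. The weaker dose is lost at the first integer above (d_weak − 1.960 × 1.744)/f. The stronger dose on its own falls below the 0.025 level at the first integer above (d_strong − 2.241 × 1.744)/f. Δ* is the larger of the two.

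For 5.4 and 4.0 with f = 0.20:

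- Weaker dose: (4.0 − 3.419)/0.20 = 2.9, so it is lost at 3.
- Stronger dose: (5.4 − 3.909)/0.20 = 7.5, so Δ* = 8.

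| Observed differences | f = 0.20: weaker dose / Δ* | f = 0.10: weaker dose / Δ* |
|---|---|---|
| 5.4 / 4.0 | 3 / 8 | 6 / 15 |
| 5.4 / 4.5 | 6 / 8 | 11 / 15 |
| 5.4 / 5.0 | 8 / 8 | 16 / 16 |
| 5.4 / 5.4 | 10 / 10 | 20 / 20 |

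**Step 5: how often the gap arises among two-dose wins.** Equal true effects do not give equal observed effects.

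| True differences, f | Δ* above weaker dose's crossing | By 3 points or more | Median Δ* / median weaker crossing |
|---|---|---|---|
| 5.4 / 5.4, 0.20 | 73.0% | 56.7% | 14 / 9 |
| 5.4 / 5.4, 0.10 | 75.1% | 66.6% | 27 / 17 |
| 4.1 / 3.2, 0.20 | 67.8% | 49.9% | 9 / 5 |

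**The case against.** **The rules do not strictly contradict each other.** One says when to run the analysis, the other when its conclusion tips, and after a two-dose win both can operate. This stands: the problem is a mismatch of success criteria. It still leaves a one-dose win outside the trigger.

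**The trigger could be read dose by dose.** SAP 5.3.2.1.1 uses similar wording for separate comparisons of each dose with placebo, and the tipping criterion accepts a one-dose result. The reading is possible, but the SAP does not state it. The one-dose figures in Step 2 matter only on the literal reading.

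**The weaker dose's crossing can be read from the planned display.** True after a two-dose win: that dose is always lost at or before Δ*, and comparisons are shown at every delta up to there. But the crossing is not defined or named as a result. After a one-dose win on the literal reading there is no display at all.

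**Copy reference still runs.** SAP 5.3.3.1 sets no success condition: "the monotone missing data will be imputed using the Copy Reference (CR) MI method for the primary analysis as a supplementary analysis". It answers a different question, since "The treatment policy strategy attempts to estimate the treatment effect irrespective of the intercurrent event", and it uses one fixed assumption instead of a range of departures from missing at random.

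**Δ* suits the either-dose hypothesis, and close doses share it.** Both points are right. At the design effect with 20% imputed, Δ* equals the weaker dose's crossing in about 27% of two-dose wins. It does not in the other 73%.

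**Many gaps would not change the reading.** Taking 5 points as an assumed benchmark, Δ* lies above it and the weaker dose's crossing at or below it in about 20% of two-dose wins at the design effect with 20% imputed, and about 11% with 10% imputed. This is a fair limit on the practical effect. The TRD3001 scenario is also only illustrative, because both arms of that study received an oral antidepressant.

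**Conclusion.** The concern holds. Followed literally, the SAP gives no tipping point for the primary estimand after a one-dose success. That outcome has a probability of about 16% under the design assumptions and about 32% at the TRD3001 differences. After a two-dose success, the one defined Δ* belongs to the stronger dose and overstates the robustness of the weaker dose's claim in about 73% of such trials at the design effect with 20% imputed.

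The tipping-point figures rest on equal imputed shares in the two active arms and a fixed standard error. They ignore any change in between-imputation variance. The logical point in Step 3 needs none of these assumptions. The primary test, its estimate and familywise error control are not affected, so this is a change that should be made but not one on which the trial's validity depends.

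**What to change.** In SAP 5.3.2.1.2:

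1. Replace the trigger with a condition that at least one dose is rejected under the Hochberg procedure.
2. For each rejected dose, report the smallest δ_A at which that dose's own Hochberg rejection is lost. When both doses are rejected, the smaller of the two values is also where the two-dose conclusion is lost.
3. Keep the current Δ*, labelled as the delta at which no dose is rejected.

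This is a change of wording and reporting only. The imputation method, the 500 datasets and the delta grid stay the same. The one downside for the sponsor is that the weaker dose's reported tipping point may be less favorable than the single Δ*.

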5.3.3. Supplementary Estimand

All components as described under Primary Estimand (Section 5.3.2) apply to the Supplementary Estimand except the strategy for addressing intercurrent events.

Intercurrent events and their corresponding strategies:

	Name of Strategy for Addressing Intercurrent Events
Intercurrent Events	and Its Description
Premature discontinuation of the randomized treatment	Treatment policy strategy: all observed values of the
with or without a switch to alternative antidepressant	endpoint are used regardless of whether or not the
treatment	participant had experienced this intercurrent event

The treatment policy strategy attempts to estimate the treatment effect irrespective of the intercurrent event. Therefore, post-treatment observations will be used in the analysis for those participants who discontinued study intervention.

5.3.3.1. Analysis Methods

This method will employ the following 3 steps:

Step 1 – Multiple Imputation (MI)

Once monotone missing datasets are created after imputing intermediate missing data using the MCMC method as described in Section 5.3.2.1.2, the monotone missing data will be imputed using the Copy Reference (CR) MI method for the primary analysis as a supplementary analysis.

Missing not at random (MNAR) is assumed for monotone missing (i.e., missing data after the occurrence of an intercurrent event under treatment policy) in the experimental intervention group, where efficacy scores are assumed as if participant had always been in the control group. MAR is assumed for missing data in the control group.

The efficacy data that is either missing or not used after the intercurrent event at a given timepoint will be imputed using the imputation model of the control group, i.e., conditional on the data observed or imputed at previous timepoints relative to the mean of the model for the control group.

This approach does not assume a sustained benefit of experimental intervention for the efficacy data that is either missing or not used after the intercurrent event, and uses an imputation method that is based on the control group distribution and the estimated correlations between time points in the control group.

Step 2 – Analysis

Same MMRM analysis as described for the primary efficacy analysis (Section 5.3.2.1.1) will be performed for each set of the adjusted fully imputed datasets.

Step 3 – Pooling

Rubin's methodology will be applied to the MMRM results from the 500 imputed datasets to produce final inferences. (Rubin 1987)

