3. SAMPLE SIZE DETERMINATION

The sample size is calculated for the full efficacy analysis set, which includes all randomized patients who meet predefined nonresponse criteria (based on MADRS assessments performed during the screening phase). A standardized treatment effect for the primary endpoint at Day 28 compared to the placebo arm of 0.45 (a treatment difference of 5.4 points for the change from baseline [Day 1 prerandomization] in MADRS total score with a standard deviation of 12) and the Hochberg procedure, with the truncation parameter equal to 1 (which results in the conventional Hochberg method with respect to the primary endpoint) to control the overall familywise error rate of 0.05 (two-sided) were used for the calculation. A 2:1:1 randomization scheme requires 71 participants per active treatment arm and 142 for the placebo arm to complete 4 weeks of treatment to achieve 85% power for each dose and 93% power to correctly reject at least one null hypothesis. Taking into consideration a 20% drop-out rate, 356 patients who meet the predefined nonresponse criteria (based on MADRS assessments performed during the screening phase) will need to be randomized in the study. The treatment discontinuation rate will be closely monitored in a blinded fashion throughout the trial.

Non-response at the end of the screening phase is based on improvement in the Montgomery-Asberg Depression Rating Scale (MADRS) total score from Week 1 to Day 1 and the MADRS total score on select screening MADRS assessments

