Parameter	Phase	Number	(label on output)	(Day)*	Point (Day)*
MADRS	Open-label	3.3	Day 35 (OL)	<=11	8
	_	3.5	Day 42 (OL)	12-18	15
		3.7	Day 49 (OL)	19-25	22
		3.9	Day 56 (OL)	26-32	29
		3.10	Day 63 (OL)	33-39	36
		3.11	Day 70 (OL)	40-46	43
		3.12	Day 77 (OL)	47-53	50
		3.13	Day 84 (OL)	54-60	57
		3.14	Day 91 (OL)	61-67	64
		3.15	Day 98 (OL)	68-74	71
		3.16	Day 105 (OL)	75 to end of OL	78
		OL final visit	Endpoint (OL)	1 to end of OL	
	F/U	4.1	Week 1 (F/U)	1 to end of F/U	7
CGI-S	Open-label	3.2	Day 31 (OL)	<=6	4
	•	3.3	Day 35 (OL)	7 - 9	8
		3.4	Day 38 (OL)	10 - 12	11
		3.5	Day 42 (OL)	13 - 16	15
		3.6	Day 45 (OL)	17 - 19	18
		3.7	Day 49 (OL)	20 - 23	22
		3.8	Day 52 (OL)	24-26	25
		3.9	Day 56 (OL)	27-32	29
		3.10	Day 63 (OL)	33-39	36
		3.11	Day 70 (OL)	40-46	43
		3.12	Day 77 (OL)	47-53	50
		3.13	Day 84 (OL)	54-60	57
		3.14	Day 91 (OL)	61-67	64
		3.15	Day 98 (OL)	68-74	71
		3.16	Day 105 (OL)	75 to end of OL	78
		OL final visit	Endpoint (OL)	1 to end of OL	
	F/U	4.1	Week 1 (F/U)	1 to end of F/U	7
Vital sign	Open-label	3.1	Day 28 (OL): Predose	1	1
J	1		Day 28 (OL): 40M		
			Day 28 (OL): 1.5H		

^{*}Relative to start date of DB phase for screening and double-blind phases, and relative to the start date of follow-up phase for follow-up phase.

^{**}If a Day 1 value is not available for Baseline (DB), the closest available value prior to randomization with a visit name of "DOUBLE-BLIND DAY 1" will be used for Baseline (DB).

a. DB (W/D subjects only) refers to data collected during the double-blind phase after subjects have discontinued study intervention.

Table 3: Visit Windows for Participants Receiving Esketamine (Open-label Treatment and follow-up phases)

	phases)				
Parameter	Analysis Phase	Scheduled Visit Number	Time Interval (label on output)	Time Interval (Day)*	Target Time Point (Day)*
		3.2	Day 31 (OL): Predose	2-6	4
			Day 31 (OL): 40M		
			Day 31 (OL): 1.5H		
		3.3	Day 35 (OL): Predose	7 - 9	8
			Day 35 (OL): 40M		
			Day 35 (OL): 1.5H		
		3.4	Day 38 (OL): Predose	10 - 12	11
			Day 38 (OL): 40M		
			Day 38 (OL): 1.5H		
		3.5	Day 42 (OL): Predose	13 - 16	15
			Day 42 (OL): 40M		
			Day 42 (OL): 1.5H		
		3.6	Day 45 (OL): Predose	17 - 19	18
			Day 45 (OL): 40M		
			Day 45 (OL): 1.5H		
		3.7	Day 49 (OL): Predose	20 - 23	22
			Day 49 (OL): 40M		
			Day 49 (OL): 1.5H		
		3.8	Day 52 (OL): Predose	24-26	25
			Day 52 (OL): 40M		
			Day 52 (OL): 1.5H		
		3.9	Day 56 (OL): Predose	27-32	29
			Day 56 (OL): 40M		
			Day 56 (OL): 1.5H		

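### Does the supplementary treatment-policy analysis replace MADRS scores that were observed after discontinuation?

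*SAP*

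**What the plan says.** SAP 5.3.3 keeps every component of the primary estimand except the strategy for intercurrent events. It lists one such event, premature discontinuation of randomized treatment with or without a switch to another antidepressant, and assigns it to treatment policy. The text below the table adds that "post-treatment observations will be used in the analysis for those participants who discontinued study intervention".

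SAP 5.3.3.1 gives the method. Intermediate gaps are filled by the MCMC step borrowed from 5.3.2.1.2, and the remaining monotone missing data are imputed by Copy Reference. In the experimental arms those data are described as "missing data after the occurrence of an intercurrent event under treatment policy". Two later sentences use a wider phrase. One instructs: "The efficacy data that is either missing or not used after the intercurrent event at a given timepoint will be imputed", using the control-group model. The other describes the assumption, saying that the approach "does not assume a sustained benefit of experimental intervention for the efficacy data that is either missing or not used after the intercurrent event".

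The borrowed section, 5.3.2.1.2, opens its code with "PROC MI DATA=INPUT NIMPUTE=500 SEED=234" and remarks, after the delta-adjustment rules, "These methods will be applied to all missing data under hypothetical strategy". In SAP 5.1.2, Table 2 windows off-treatment MADRS records in a separate phase, DB (W/D subjects only). Its footnote says the label "refers to data collected during the double-blind phase after subjects have discontinued study intervention".

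**The concern.** A score observed after discontinuation cannot be both kept and imputed. Under treatment policy the words *not used* seem to have content only if some observed scores are set aside.

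The cross-reference adds to the doubt. It leads to a dataset with a generic name, in a section written for the hypothetical strategy, under which Protocol 9.4.2 leaves post-treatment observations out of the primary analysis. A programmer who reused that input could begin with off-treatment scores already removed, and 5.3.3.1 does not say that the separate Table 2 phase is to be added.

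At stake is the one planned inferential analysis in which these scores can enter. Protocol 4.1 asks participants who stop dosing to attend through Day 28 so that such data exist. Under the misreading, a reference-based analysis of on-treatment data would be reported under a treatment-policy label.

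**Working it through.** **Which reading do the passages support?**

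1. *The rule.* SAP 5.3.3 states it twice: in the estimand table (all observed endpoint values are used) and in the sentence beneath it.
2. *The imputed set.* 5.3.3.1 applies Copy Reference to monotone missing data and defines these as missing after the event under treatment policy. A recorded score is not missing.
3. *The unused set.* Observed data go unused only when an intercurrent event is handled by a strategy that drops them. One event is listed, and its strategy drops nothing, so the set is empty.
4. *The two sentences.* Only one of them instructs imputation. The other describes an assumption and adds no rule.
5. *The input.* INPUT is a placeholder in schematic code whose VAR and CLASS statements are also left open. The estimand determines its content.
6. *The hypothetical-strategy remark.* It belongs to the delta-adjustment method for the primary estimand. 5.3.3.1 borrows only the MCMC step and then states its own strategy.
7. *Table 2.* Off-treatment MADRS records have the same day ranges as on-treatment ones (2-4, 5-11, 12-18, 19-24, 25 to end of phase), so they can enter a Day 28 analysis directly.

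The SAP version history says that 5.3.3 was expanded from the last paragraph of 5.3.2.1.2 to give more detail on the treatment-policy estimand. That fits wording carried over from a section where off-treatment scores are indeed unused.

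**What would a misreading cost?**

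Section 5.3.3.1 has no design figure to reproduce, so the scale comes from SAP section 3: effect 5.4, SD 12, 142 placebo and 71 per dose completing, 20% drop-out.

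- Sample size: 71/0.8 = 88.75, rounded up to 89; 142/0.8 = 177.5, rounded up to 178; 178 + 89 + 89 = 356, as stated.
- Power: simulating Hochberg with a shared placebo arm (1,000,000 runs) gives 85.9% per dose and 93.9% for at least one dose, against the stated 85% and 93%.
- Planned standard error: 12 × √(1/71 + 1/142) = 1.74.

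Shift in the treatment difference, scores used minus scores replaced (negative favours esketamine):

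shift = f × r × (dE − dP)

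Here f is the share discontinuing (0.20, the planned drop-out), r the share of those with an observed Day 28 score (assumed), and dE and dP the observed minus imputed means among esketamine and placebo discontinuers (assumed 0 or −5.4).

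| Assumption | r = 1 | r = 0.5 |
|---|---|---|
| Equal gaps in both arms | 0 | 0 |
| Only esketamine discontinuers better than imputed | 0.20 × 1 × (−5.4) = −1.08 | −0.54 |
| Only placebo discontinuers better than imputed | 0.20 × 1 × (+5.4) = +1.08 | +0.54 |

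The shift scales with f. At 5% discontinuation the largest value is 0.05 × 5.4 = 0.27.

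Copy Reference conditions on earlier scores, so it carries forward part of any benefit already seen. With a common correlation of 0.6 and three prior visits the carried share is (3 × 0.6)/(1 + 2 × 0.6) = 1.8/2.2 = 82%. On a prior benefit of about 4 points that is about 3.3, and 0.20 × 3.3 is about 0.65 points. A simulation built this way (correlation 0.4 to 0.8, 20% stopping at random after Day 15, all observed) gives −0.57 to −0.37 if only esketamine discontinuers do better off treatment, +0.50 to +0.70 if both arms fare alike, and +1.59 to +1.77 if only placebo discontinuers do better.

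**The case for a change.** The strongest case for a change is that a SAP should not depend on the reader working out that a category is empty. This analysis is the only inferential use of data that participants are asked to keep providing. The sponsor supplied code and a seed for the imputation model to make it clearer, and the treatment-policy input deserves equal care. The conditional calculation also shows that, when both arms fare alike off treatment, replacing the scores would favour esketamine. Deleting two words costs almost nothing.

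Part of this stands. The phrase is loose, the cross-reference could be tidier, and striking the words in both sentences would do no harm. But a misreading would have to override the estimand table, the sentence below it and the definition within 5.3.3.1 itself. A deletion would therefore confirm what the text already requires and leave the result unchanged.

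One further detail is left unstated: how to treat a gap before a later observed off-treatment score. The SAP defines intermediate missing data as lying between non-missing observations and sends them to the MCMC step under missing at random. Applied to a dataset that keeps off-treatment scores, that definition covers such a gap. Analysts can fill it sensibly, and deleting *not used* would not settle it either way.

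**Conclusion.** No change follows. The wording is a clerical leftover in a supplementary analysis outside the Hochberg family. Section 5.3.3 states the controlling rule twice, and 5.3.3.1 confines Copy Reference to data missing under treatment policy, so the plan as written yields the intended estimate.

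Read that way, the effect on results is nil. Under the misreading the shift would be 0 to 1.08 points in either direction by the simple formula, and −0.57 to +1.77 in the simulation, compared with a standard error of 1.74. These figures assume 20% discontinuation, full observation at Day 28 and off-treatment differences as large as the planned effect. The documents give neither the share observed nor the off-treatment outcomes, so they support no particular size or sign.
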